## 6. STUDY SETTING

The clinical evaluation study [Part A] will be performed in secondary care at eight acute Trusts in England.

Clinical sites include:

- Nottingham University Hospital NHS Trust
- University College London Hospitals NHS Trust
- Mid Yorkshire Hospitals NHS Trust
- University Hospitals Birmingham NHS Trust
- East Suffolk and North Essex NHS Trust
- University Hospitals of Leicester NHS Trust
- St. Georges University Hospitals NHS Trust
- United Lincolnshire Hospitals NHS Trust

### Part B

No separate recruitment will be required for the health economic analysis

SHORT TITLE/ACRONYM: LungIMPACT  
IRAS: 317009

## SAMPLE AND RECRUITMENT

### Part A

#### 7.1 Eligibility Criteria

##### 7.1.1 Inclusion criteria

- CXR referred from primary care
- Age  $\geq$  18 years
- Anteroposterior (AP) or Posteroanterior (PA) view

##### 7.1.2 Exclusion criteria

- Age <18 years
- CXR referral not from primary care
- Lateral X-ray view of the chest

### Part B

#### 7.2 Eligibility Criteria

No separate recruitment will be required for the health economic analysis

## 7.3 Sampling

[figure not shown]
### 7.3.1 Size of sample

#### Part A

The primary endpoints of this study are the difference in median time between CXRs suspicious for lung cancer and CT chest and the difference in median time to lung cancer diagnosis between routine reporting with AI available and AI support at the time of CXR acquisition and prioritisation for immediate review of CXRs reporting arms. The expected prevalence of lung cancer in this cohort (primary care referrals for CXR) is 0.6%. Thus for 150,000 CXRs this will lead to the detection of about 900 cancer cases. Using data from previous work, the median time to lung cancer diagnosis was 63 days in the standard reporting group and if we use a conservative reduction of 10 days, with 95% power we would need 265 cases per group (Table 6). Most likely, the time to diagnosis is going to be greater than 10 days such that the sample size will give us plenty of power to detect a difference between the groups on time to diagnosis. Considering that 30% of lung cancer patients die within 90 days of diagnosis, a 10 or more-day difference is clinically significant (Table 7).

The co-primary endpoint of this study is time between an abnormal CXR that is suspicious for lung cancer to CT chest. Based on the NHS Diagnostic Imaging Dataset between 4,000-4,500 CT chest scans referred from primary care are expected during the study period at the clinical sites, median time for England (CT chest request to test) is 14 days, but this data is not segregated between urgent scans and those that are routine or for follow up. The mean and standard deviation of time between abnormal CXR and CT chest are not known for either the intervention (AI support at the time of CXR acquisition and prioritisation for immediate review of CXRs) or routine CXR reporting with AI available. Cohen's d (effect size) was used to estimate sample size with power 0.1, 0.3 and 0.5 are considered small, moderate and large effect size. Assuming approximately equal distribution (Nnotification:Nstandard as 0.8 to 1.2) of the number of scans taken, the estimated 4,000 CT chest scans will give adequate power to detect even the smallest effect size (Cohen's d = 0.1; Figure 2). We have defined a clinically meaningful difference in time from abnormal to CT chest as 3 days, using the maximum time recommended in the NOLCP.

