#### **4.2 Outcome**

The outcomes can be classified as those related to the effectiveness of the AI support at the time of CXR acquisition for immediate review (immediate report and straight to CT where appropriate; Part A) and those related to the health economic assessment [Part B]. A discrete choice experiment will be conducted to inform the health economic analysis, led by University College London (UCL) health economists [Part C] and will be reviewed by UCL ethics. Patient experience and communication preferences [Part D] and staff engagement [Part E] are components of the larger programme of work and independent evaluation, performed in partnership with UCLPartners and City University. City University ethical approval is already in place for the staff engagement [Part E reference ETH2223-0030 and will be applied for [Part D]. Workstreams C-E are part of the larger programme and are outside the scope of this protocol.

Outcomes related to clinical evaluation [Part A]

The primary outcomes related to clinical evaluation (Part A) are:

A1. The difference in time (in days) to the diagnosis of lung cancer for patients who have CXRs with an AI support at the time of CXR acquisition and prioritisation for immediate review and those that have no immediate read but the AI read is available at the time of reporting.

A2. The difference in time (in days) to CT for patients with suspected lung cancer who have CXRs with an AI support at the time of CXR acquisition and prioritisation for immediate review and those that have no immediate read but the AI read is available at the time of reporting.

Rationale for choice of two primary outcomes:

A strength of the trial is the multisite, pragmatic design of the clinical evaluation. Pre-trial review has demonstrated heterogeneity in radiology workflows (CT scanner capacity, community sites without CT on-site, CT reporting times), referral routes and lung cancer pathway design (respiratory review prior to CT, virtual triage) at the clinical sites. Time to lung cancer diagnosis is clinically meaningful and time to CT will be the least affected by the heterogeneity inherent in this study. Both outcomes will be considered primary and there are no hierarchy among these two. A sub-group analysis will be undertaken for these endpoints by sites and time periods (quarterly interval).

Other steps in the patient pathway for the diagnosis of lung cancer are included as secondary outcomes. The secondary outcomes are:

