## 5. STUDY DESIGN AND METHODS OF DATA COLLECTION AND DATA ANALYSIS

### Part A: Clinical Evaluation

[figure not shown]
This is a prospective, multi-centre healthcare service delivery study with the primary objective of assessing the effectiveness of AI immediate read and worklist prioritisation for immediate review on the time to diagnosis of lung cancer and the time to CT chest following abnormal CXR. The study will be conducted over a 12-month period at eight NHS Trusts in England. qXR, a class IIa CE certified deep learning algorithm already in routine clinical use in some NHS Trusts, will be used in this study. All patients in the study will have their CXRs read by qXR. The only difference is the timing of the information from the AI. The process adopted in radiology departments is that the patient attends for a CXR and it is performed by a radiographer. The radiographer may, at their discretion flag abnormalities that may require further action and this may result in a CT scan being done, sometimes on the same day as is a preferred option in the NOLCP. The radiographer flag can also happen for any other (non-cancer) findings where they consider that action is potentially needed. The usual clinical pathway will be followed where action is confirmed to be necessary or optimal. Where there is no flag, the CXR is later reported by a radiologist or reporting radiographer. This study is testing whether having an AI immediate tag influences that process and shortens time to diagnosis. The pathway is shown on the study flowchart (page 10).

AI clinical decision support will be available to the reporting practitioner (consultant radiologist, specialist registrar or reporting radiographer) for all CXRs. The intervention is the timing of the CXR alert from the AI, on intervention (worklist prioritisation for immediate report) and non-intervention (routine reporting time) days. On intervention days, an active notification will be sent to the worklist for any 'qXR-suspected-abnormal cases, so these can be prioritised for immediate reporting. Pre-allocation to intervention (qXR AI support at the time of CXR acquisition and worklist prioritisation for immediate CXR review) and routine care (normal reporting with

SHORT TITLE/ACRONYM: LungIMPACT  
IRAS: 317009

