qXR read available) will occur using random sampling (Monday – Friday when routine imaging is performed). All patients over 18 years will have qXR decision support available. Patients will receive routine care, no additional diagnostic tests will be performed. Data will be collected from existing routine clinical data sources. All imaging (CXR or CT) will be performed as part of routine care, and no additional radiation exposure will be required. The reporting practitioner will have the AI decision support information for all cases and all days, the intervention is only the timing of the AI information (immediate reporting or with usual reporting). The reporting practitioner can choose to accept the alert and refer the patient for CT chest and/or referral onto the lung cancer pathway where appropriate. Patients who are referred for CT will follow the current CT and post-CT pathways of the participating clinical sites, which may include placing them on a cancer pathway. On non-notification days, the AI tool information will be available at the time the CXRs are reporting by the reporting practitioner (Figure 1). The PACS will have both the original image and qXR secondary capture showing the AI attention point.

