## **7.4 Recruitment**

### Part A

The clinical evaluation study [Part A] will not directly recruit patients; it is an evaluation of health service delivery. Patients will have their pseudonymised data collected to provide the outcomes. No additional or different tests will be performed, and all the reporting practitioners currently report CXRs in clinical practice. The comparative aspect of the study is the timing of the AI flagging of a possible CXR abnormality. The intervention can be considered as an additional prompt to consider a further test by the person providing the CXR report (CT scan) but it is not known if this improves the clinical pathway. All patients referred for a CXR by primary care will receive the usual standard of care and referral pathways for each of the eight clinical sites, including the AI decision support, the only difference is the timing of CXR reporting. The intervention is the same at each institution with block randomisation to the intervention or no intervention by day.

SHORT TITLE/ACRONYM: LungIMPACT  
IRAS: 317009

Part B

No separate recruitment will be required for the health economic analysis

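### The A2 analysis set (time to CT) is worded three ways, with no stated owner or time for the suspicion call, so the alert may change who enters it; its power also rests on a mixed pool of CT scans

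*Protocol*

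**What the plan says.** Section 4.2 makes A2 one of two primary outcomes of equal rank: "The difference in time (in days) to CT for patients with suspected lung cancer". Section 5 (Part A) gives the objective as "the time to CT chest following abnormal CXR". Section 7.3.1 has "the difference in median time between CXRs suspicious for lung cancer and CT chest" and, one paragraph later, "time between an abnormal CXR that is suspicious for lung cancer to CT chest"; its 3-day meaningful difference is again counted from an abnormal film. None of these places says whether suspicion is the judgement of the acquiring radiographer, the reporter, qXR or the weekly panel.

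Allocation is by day (Section 7.3.2). Section 7.4 says of the alert: "The intervention can be considered as an additional prompt to consider a further test by the person providing the CXR report (CT scan" (the bracket closes there). Two features apply in both arms. Section 5 states that "The reporting practitioner will have the AI decision support information for all cases and all days", and flagged cases that were not pursued are reviewed, with recall of suspicious ones (Section 5, Table 5; weekly in Section 8.1).

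A2 is sized on 4,000 of the 4,000 to 4,500 primary-care chest CTs expected at the sites, which the text calls adequate for Cohen's d = 0.1. Of the source dataset it says that "this data is not segregated between urgent scans and those that are routine or for follow up".

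**The concern.** A median compared between arms has the protection of randomisation only if entry to the set cannot depend on the arm. Every CXR on a randomised day meets that condition. A set defined by a human judgement at reporting does not, because that judgement comes after allocation and the alert is meant to prompt it.

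The protocol itself treats a change in who is referred as an open question. Section 4.1 asks whether the intervention alters the number of non-cancer urgent referrals, Section 4.2 counts urgent referrals as an outcome, and Section 2 reports a trend to fewer urgent referrals under immediate reporting in the earlier single-site trial. If the mix of patients entering A2 differs by arm, a primary result could be created or masked by that difference.

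The wordings also describe sets of very different size, and the number of scans used for power describes none of them exactly.

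**Working it through.** **1. How far apart the definitions are.** Section 7.3.1 expects 40% of primary-care CXRs to be abnormal: 0.40 × 150,000 = 60,000. Against 4,000 CTs that is 4,000 / 60,000 = 6.7%. If those CTs are all the relevant ones, a median over all abnormal CXRs would never be reached, and any reported median would be conditional on having a scan. The suspicious set is narrower and is not counted anywhere.

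**2. The protocol's power statement.** Inputs: d = 0.1 and N = 4,000 (Section 7.3.1). Alpha is not stated; two-sided 0.05 is assumed. Power = Φ(d√(N/4) − 1.96) = Φ(3.16 − 1.96) = 88.5% at 1:1, and 88.2% and 88.3% at ratios 0.8 and 1.2. At alpha 0.025 it is 82%. The claim of adequate power therefore reproduces, provided that all 4,000 scans belong to the A2 set.

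**3. Power if only part of the pool qualifies (shares assumed).**

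| Share | N | Power at d = 0.1 |
|---|---|---|
| 100% | 4,000 | 88.5% |
| 75% | 3,000 | 78% |
| 50% | 2,000 | 61% |
| 25% | 1,000 | 35% |

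In the other direction, Section 7.3.1 expects 900 cancers and Section 2 cites cancer yields of 12% and 18% in the earlier trial. If cancers arose at those yields from urgent referrals, there would be 900 / 0.18 = 5,000 to 900 / 0.12 = 7,500 referrals.

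**4. Effect of a change in case mix alone.** Assume identical times to CT in both arms for patients who would be suspected in either, exponential with median 14 days. The 14 days is England's CT request-to-test median in Section 7.3.1, borrowed because no CXR-to-CT figure is given. Add to the alert arm a fraction x of extra patients with a same-day CT. The new median m solves (F(m) + x)/(1 + x) = 0.5, so F(m) = 0.5(1 − x).

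- x = 5%: m = 13.0 days; x = 10%: m = 12.1 days.
- For m = 11: F(11) = 1 − 2^(−11/14) = 0.420, so x = (0.5 − 0.420)/0.5 = 16%.
- Lognormal times with the same median need 16% (sigma 1.2) to 31% (sigma 0.6).
- If the extras have a median of 3 days instead of a same-day CT, 19% is needed (exponential).
- Losing the slowest 16% of the set on alert days has the same effect: F(m) = 0.5 × 0.84 = 0.42, so m = 11.

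In 1,000 simulated trials with 2,000 per arm plus the extras, a rank test was significant in 5.6% of trials with no extras, 18% with 2%, 74% with 5% and 100% with 10%.

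**5. What a set based on the qXR flag would cost.** Primary-care sensitivity 96% and specificity 80% (Section 2) with 40% abnormal give a flag rate of 0.40 × 0.96 + 0.60 × 0.20 = 50.4%, or about 37,800 flagged CXRs per arm. If all 4,000 CTs follow flagged CXRs, 2,000 / 37,800 = 5.29% are scanned in each arm. CT by day 3 is then 5.29% × (1 − 2^(−3/14)) = 0.73% with a 14-day median and 5.29% × (1 − 2^(−3/11)) = 0.91% with an 11-day median. Power for that contrast is 79%. With 2,000 or 1,000 such CTs it is 49% or 28%. No allowance is made for randomisation by day.

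**The case against.** The strongest reply is that only the timing of the AI output differs. The reporter sees it on every day, and flagged cases left unpursued are reviewed weekly in both arms and recalled if suspicious. Table 5 covers all discordant nodules, opacities, cavities, consolidations, hilar enlargements and pneumothoraces. The step 4 scenario needs patients who would have had no CT on a control day, which is what the recall should prevent. A control patient recalled late is a genuine delay that A2 should capture. Section 5 also commits to measuring changed radiographer behaviour by arm. This stands as a reason to expect a smaller shift. It does not exclude one, since timing is the intervention and some findings are reviewed only in a sample.

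It can also be said that Section 8.6 puts all cases in the primary analysis and that handling of patients without a CT belongs in the SAP. That is fair on handling. It does not settle which of three differently worded sets is meant.

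A reader might infer that A2 is the set the reporter called suspicious. The protocol does not say so; the unassigned call is the defect. A reader might also take the 4,000 scans to be unrelated to the trial. They are primary-care chest CTs at the study sites, so the pool is mixed but overlapping.

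**Conclusion.** The point holds in this form: a co-primary endpoint has three differently worded sets, the suspicion call has no stated owner or time, and if it is made at reporting the alert can influence membership. A shift in the median from case mix alone is possible, not shown. Its size is unknown, and the 16% (16 to 31% over the lognormal shapes tried) rests on an assumed distribution and a borrowed 14-day median.

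A stronger reading would be that the median could fall with nobody scanned sooner. That does not follow, because the added patients are themselves scanned sooner. What follows is that no patient who would be suspected in either arm need be scanned sooner.

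Nor do the documents show A2 to be underpowered. The stated power reproduces at about 88% if all 4,000 scans qualify. The falls to 78%, 61% or 35% rest on assumed shares, and the true set could exceed 4,000.

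**What to change.** - Use one definition of A2 in Sections 4.2, 5 and 7.3.1, and state whose output or judgement defines the set, and when.
- Base A2, or at least a prespecified key analysis beside it, on the qXR output at acquisition. qXR reads every CXR in both arms, its finding is already in Table 6, and it cannot depend on the day's allocation. Preferably limit the set to a prespecified list of cancer-relevant qXR findings, since the 29 findings that trigger prioritisation include scoliosis and rib fractures.
- Keep patients without a CT in the denominator and compare the cumulative incidence of CT, for example by day 3, matching the 72-hour standard the protocol cites.
- Report suspicious reports and CTs per 1,000 CXRs by arm beside A2.
- State A2 power as conditional on the number of qualifying patients, over a range.

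The cost is an amendment and some dilution: about 79% power on the full flagged set in the best case of step 5, and less if fewer CTs follow flagged CXRs. That makes the full flagged set debatable as the sole primary set. Scan dates must also be obtained for flagged patients, because Table 6 lists referral to CT and the date of the CT report but no CT scan date.

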## 2. RATIONALE

Recently published work performed by members of the study team (Woznitza *et al radioX*) found that immediate radiographer CXR reporting and triage straight to CT significantly reduced time to diagnosis of lung cancer by almost half from a median of 63 days from CXR, to 32 days, ( $p = 0.03$ ) compared to routine CXR reporting once the patient has left the department. This demonstrated that immediate CXR reporting pathway is feasible and beneficial. A trend for fewer urgent referrals being made to respiratory medicine was also found, with a higher proportion of cancer diagnoses made in those with immediate CXR reporting (18% vs 12%;  $p = 0.12$ ). What is unclear is if the findings of this single site study with a small number of lung cancers ( $n=49$ ) is replicable in other settings or scalable at a system level. Benefits of other interventions successful in single clinical sites are not always transferrable when evaluated in multi-site trials for many reasons, including implementation barriers. Since immediate reporting has resource and workforce implications, it is crucial that if immediate reporting is to be rolled out nationally, it is done so based on robust evidence.

Nearly two million CXRs referred from primary care are performed annually in England and CXR is one of the most frequently performed investigations. Not all CXRs will have findings suspicious for cancer, and this may be an incidental finding (CXR requested for a reason other than suspected cancer). One way to optimise the limited imaging workforce could be to use an artificial intelligence (AI) tool as assistance in decisions to triage CXRs referred from primary care that have findings suspicious for lung cancer. This would enable immediate flagging and reporting to be prioritised for patients most likely to benefit from a same-day CT scan. AI clinical decision support was identified as one way to reduce observer variability in CXR interpretation by NICE as well as supporting current NICE care pathways for suspected cancer, chronic obstructive pulmonary disease, cystic fibrosis, idiopathic pulmonary fibrosis and tuberculosis.

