**Table 5. Proportion of discordant cases to undergo thoracic radiologist review**

Abnormality	Proportion
Blunted CP	1,000 CXRs
Cardiomegaly	1,000 CXRs
Cavity	All
Consolidation	All
Fibrosis	20%
Hilar enlargement	All
Nodule	All
Opacity	All
Pleural effusion	20%
Pneumothorax	All

Cases that are flagged (in either arm) as positive but not taken up for further testing will be reviewed and patients with CXRs suspicious for cancer will be called back for further testing. This is done in both arms of the study and is an additional safety check; this is routine clinical practice. The proposed review/recall methodology is a form of radiology peer review, advocated as an effective method of quality assurance. Double reading and recall where appropriate is not novel, for example it is used as standard as part of the breast cancer screening programme.

Variables collected:

Only data collected for routine care will be used and no additional data will be collected. No patient identifiable data will be available outside of the clinical care team; all data will be pseudonymised prior to analysis by the independent statistician. qTrack will be used as the trial management database; it cannot be accessed by the Qure Team. Variables are presented in Table 6.

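### The claim of ample power for time to diagnosis (A1) fails on the protocol's own inputs and rests on a gain of 10 days or more that nothing supports for this trial's contrast

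*Protocol*

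**What the plan says.** Section 7.3.1 expects about 900 lung cancers (0.6% of 150,000 chest X-rays). For A1 it starts from "63 days in the standard reporting group and if we use a conservative reduction of 10 days" and states that "with 95% power we would need 265 cases per group". It then says that the gain will most likely exceed 10 days, so that "the sample size will give us plenty of power to detect a difference between the groups on time to diagnosis".

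Table 7, in the same section, gives total samples for five rows: 38 to 28 days (402, 90% power), 32 to 22 (312, 90%), 63 to 53 (1,518 for 90% and 1,134 for 80%) and 20 to 10 (102, 90%). Every row has a 10-day gain.

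Section 2 gives the source of the 63 days: a single-site trial with 49 lung cancers. Immediate radiographer reporting with triage straight to CT cut time to diagnosis "from a median of 63 days from CXR, to 32 days", "compared to routine CXR reporting once the patient has left the department". Section 2 also says it is unclear whether that result can be replicated or scaled.

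In this trial, section 4.2 defines the A1 control group as "those that have no immediate read but the AI read is available at the time of reporting". Section 5 says that the intervention is only the timing of the AI information. It sends AI flags rejected by the reporter to weekly expert review, and has flagged cases that were not pursued reviewed and, if suspicious, called back: "This is done in both arms of the study and is an additional safety check".

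**The concern.** The power statement leans on a borrowed effect. The earlier trial compared immediate with routine reporting, and its description mentions no AI in either arm. LungIMPACT compares an immediate AI alert with the same AI read seen at routine reporting, with the same review and recall behind both. Neither the 63-day median nor a gain above 10 days is shown to carry over. For the CT endpoint, section 7.3.1 admits that the mean and standard deviation are unknown for both arms, including routine reporting with AI available. It gives no such caveat for A1.

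The statement can also be tested against figures in the same section, since Table 7's samples for 63 versus 53 days exceed the cancers expected. A reader who trusts the text would expect A1 to be well powered and could over-interpret a non-significant result.

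**Working it through.** **Inputs.** Expected cancers D = 900, medians 63 and 53, and Table 7's hazards and totals, all from section 7.3.1. Assumed: 1:1 allocation, exponential times, two-sided 5% (no alpha is stated), every cancer counted as an event, and no allowance for clustering by randomised day.

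**1. Reproduce Table 7.** Freedman: D = (z_α/2 + z_β)² × [(1 + HR)/(1 − HR)]². With the rounded hazards, HR = 0.011/0.013 and the bracket is 0.024/0.002 = 12, so its square is 144.

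- 90% power: 10.507 × 144 gives 1,514 (Table 7: 1,518).
- 80% power: 7.849 × 144 gives 1,131 (Table 7: 1,134).

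The other rows give 397, 307 and 98 against 402, 312 and 102. Table 7 therefore fits a two-sided 5% log-rank calculation.

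**2. The figure in the text.** For 63 versus 53 days at 95% power, Schoenfeld, D = 4(z_α/2 + z_β)²/(ln HR)², gives 1,740 in total (Freedman 1,749; 1,863 and 1,872 with rounded hazards). One-sided versions give 1,450 to 1,559. The text's 265 per group (530 in total) is not reproduced: 530 events give 51% power, or 63% one-sided. It also conflicts with Table 7's 759 per group at 90%.

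**3. Power with 900 cancers.** Power = Φ(|ln HR| × √D/2 − 1.96), with √900/2 = 15.

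- 63 versus 53: ln(63/53) = 0.1728; 15 × 0.1728 − 1.96 = 0.63; power about 74%.
- With Table 7's rounded hazards: about 71%. One-sided 5%: about 83%.
- Expected cancers as a share of Table 7's need: 900/1,134 = 79% (80% power) and 900/1,518 = 59% (90% power).

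**4. Gains below 10 days, which Table 7 does not examine (900 cancers).**

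| Control median | 5-day gain | 7-day gain | 10-day gain |
|---|---|---|---|
| 63 | 24% | 42% | 74% |
| 38 | 56% | 86% | >99% |
| 32 | 72% | 96% | >99% |

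**5. Detectable difference with 900 cancers.** Ratio of medians = exp[2(1.96 + z_β)/√900], which is 1.205 at 80% power and 1.241 at 90%. Gain = control median × (1 − 1/ratio).

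| Control median | 80% power | 90% power |
|---|---|---|
| 20 | 3.4 days | 3.9 days |
| 32 | 5.5 days | 6.2 days |
| 38 | 6.5 days | 7.4 days |
| 63 | 10.7 days | 12.2 days |

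**6. What AI and recall in both arms could do.** The documents give no figure, so both directions are shown from the 63 versus 53 base.

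- Both medians 3 days shorter (60 versus 50): 15 × ln(60/50) − 1.96 = 0.77; power about 78%.
- Only the control 3 days shorter (60 versus 53): 15 × ln(60/53) − 1.96 = −0.10; power about 46%.

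**The case against.** The strongest reply is that the earlier contrast is close to this one. Both concern the timing of reporting, and section 7.4 says that timing is the only difference here. An AI read seen at routine reporting does not bring the report forward. Recall covers only flags that were not pursued, and Table 5 merely samples some findings. Planning for 10 days when the earlier trial saw 31 (63 − 32) is a discount of about two thirds, so calling it conservative against the cited evidence is defensible. Table 7 already tries shorter control medians, and at 20 to 38 days 900 cancers detect gains well below 10 days. Sections 4.2 and 7.3.1 both name the AI-available comparator.

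Most of this stands. A reader might infer that AI and recall in the control arm must erode the difference, leaving the trial with little power for a timing-only effect. The documents do not support that. The AI read and recall apply to both arms, their effect on either median is not quantified, and step 6 shows that power can move either way. That the earlier trial used no AI is itself inferred from its description in section 2.

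The reply does not rescue the power sentence. Similarity of design does not establish a gain above 10 days, section 2 itself doubts that the earlier result will transfer, and the shortfall at 63 days does not depend on the comparator.

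**Conclusion.** The power claim for A1 is wrong as written. At the medians the text uses, 900 cancers give about 74% power under a two-sided 5% test with 1:1 allocation. That is below the 80% for which Table 7 requires 1,134. A one-sided 5% test would give about 83%, still short of the 95% in the text.

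The expectation of more than 10 days has no stated support for a contrast in which both arms have the AI read and recall, and Table 7 examines no smaller gain. Whether the true gain is smaller is not known from the documents. Nor do they show that the trial is underpowered throughout: at control medians of 20 to 38 days, gains of 3.4 to 6.5 days are detectable with 80% power. The weakness lies near 63 days and for small gains.

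**What to change.** In section 7.3.1:

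- Delete the sentence that expects more than 10 days and claims ample power.
- State that the 63-day median and the 63-to-32-day effect come from the earlier trial's routine-reporting comparator, and that the gain for this trial's comparator is unknown.
- Add to Table 7 the difference detectable with 900 cancers at control medians of 20, 32, 38 and 63 days, for 80% and 90% power, as in step 5, with alpha and allocation stated.

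The 265-per-group figure should be reconciled with Table 7 in the same edit, since it sits in the adjoining sentence. The word conservative can stay, and no further statement of what A1 estimates is needed on this ground, because sections 4.2 and 7.3.1 already name the comparator.

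The cost is wording and one table, with no extra patients or data. The downside is a less favourable stated power at 63 days.
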